16.3. Endpoints

16.3.1. Primary Endpoint

The primary endpoint for evaluation of efficacy is:

- The estimate of the OS which is performed by estimating the hazard rate based on the accrual and follow-up of all treated subjects.
- The per protocol population will be followed from the first date of treatment up to years for overall survival. Estimates of the single arm hazard rate will be determined and compared with historical control estimates

The primary endpoint is to determine the safety and efficacy of intratumoral [REDACTED] (Ad-RTS-hIL-12) and oral (PO) veledimex (RTS activator ligand) in combination with cemiplimab-rwlc (Libtayo®) based on the estimate of Overall Survival (OS) when treating subjects with recurrent or progressive glioblastoma.

16.3.2. Secondary Endpoints

Secondary endpoints include:

- Overall survival rate will be determined at 6, 12, 18 and 24 months
- PFS, and rate of pseudo-progression (PSP) of Ad-RTS-hIL-12 + veledimex when administered in combination with cemiplimab-rwlc
- ORR of Ad-RTS-hIL-12 + veledimex when administered in combination with cemiplimab-rwlc at 6, 12, 18 and 24 months
- Tumor response rate of Ad-RTS-hIL-12 + veledimex when administered in combination with cemiplimab-rwlc at 6, 12, 18 and 24 months

16.4. Safety Evaluation

Safety will be evaluated in using National Cancer Institute (NCI) Common Terminology Criteria for Adverse Events (CTCAE) v5.

Safety will be evaluated based on frequency and severity of adverse events (AEs), Serious adverse events (SAEs), laboratory abnormalities, electrocardiograms (ECGs), vital signs and physical/neurologic examination findings. The severity of AEs will be graded using National Cancer Institute (NCI) Common Terminology Criteria for Adverse Events (CTCAE) v5. The reporting period of safety data will be from the date of ICF signature through 90 days after the last dose of any study drug.

16.5. Efficacy Evaluation

- The primary analysis for efficacy is based on the per protocol population.
- Secondary analyses for all efficacy endpoints will be based on the Safety population.

The primary endpoint for evaluation of efficacy is:

- the estimate of the OS which is performed by estimating the hazard rate based on the accrual and follow-up of all treated subjects.
- The per protocol population will be followed from the first date of treatment up to 24 months for overall survival. Estimates of the single arm hazard rate will be determined and compared with historical control estimates

All populations for analyses and the types of analyses to be performed will be defined in more detail in the statistical analysis plan (SAP).

Secondary endpoints include:

- The OS rate will be determined for 6, 12, 18 and 24 months using a binomial estimate of subjects surviving for at least the amount of time established by the cutpoint.
- PFS, and rate of pseudo-progression (PSP) of Ad-RTS-hIL-12 + veledimex when administered in combination with cemiplimab-rwlc will be determined based on the investigator assessment
- ORR of Ad-RTS-hIL-12 + veledimex when administered in combination with cemiplimab-rwlc at 6, 12, 18 and 24 months will be determined based on an investigator assessment.
- Tumor response rate of Ad-RTS-hIL-12 + veledimex when administered in combination with cemiplimab-rwlc at 6, 12, 18 and 24 months

16.6. Analyses

16.6.1. Baseline Characteristics

Demographic and baseline disease characteristic data will be summarized. Data to be tabulated will include at least demographic features such as sex, age, and race, as well as disease-specific status and medical history.

Categorical data will be summarized using counts and percentages for a particular category. For continuous variables, the number of subjects with non-missing values, mean, median, standard deviation, minimum, and maximum values will be presented.

16.6.2. Safety Analyses

The safety population will be used to perform safety evaluations for all safety variables.

Safety evaluations will be based on the incidence, intensity, and type of AEs and SAEs. Clinically significant changes in the subjects' physical examinations, vital signs, and ECG evaluations, and abnormal laboratory values will be captured as AEs. Safety will also be assessed based on medical history and prior/concomitant medications.

The safety evaluation period extends from the date the patient signs the ICF until 90 days after the last dose of study drug, unless the patient discontinues the trial due to one of the following reasons:

- Documented progression
- Symptomatic deterioration also denoted as symptomatic progression
- AEs that the investigator feels will subsequently make the subject noncompliant with the protocol planned Schedule of Study Procedures
- Loss to follow-up
- Noncompliance with the protocol
- Other reason not listed above

All treatment-emergent AEs will be coded using the Medical Dictionary for Regulatory Activities (MedDRA) and will be tabulated by number and percent of subjects, and according to relationship to the study drugs, severity, and seriousness. Treatment-emergent is defined as any AE that occurs during or after administration of the first dose of study drug through the evaluation period for safety defined above, regardless of relationship to study drug; or any event that is present at baseline that worsens in intensity or is subsequently considered to be drug related by the investigator. Deaths, SAEs, and AEs resulting in study discontinuation will be listed.

Subjects who discontinue the trial as defined above will be followed for safety up to 90 days after discontinuation and until all safety events that have started during the safety evaluation period are classified as resolved or the end of the study is reached. After the conclusion of the safety evaluation period is triggered by a discontinuation event, the subject continues to be followed only for OS.

Listings of vital signs and physical examination data will be presented by visit.

16.6.3. Overall Survival

OS is defined as the duration of time from the first dose of study drug (Day -7) to the date of death or to the last follow-up contact date if the subject has not died, in which case the subject is censored if still alive up to 2 years from the first dose of study drug received.

16.6.4. Tumor Response Analyses

Investigator assessment of ORR and PFS will be determined according to iRANO criteria. A two-sided confidence interval will be computed for the ORR. PFS and OS will be estimated using the Kaplan-Meier method for appropriately-sized subject groups.

Following completion of the study, best response will be determined for each subject in accordance with iRANO guidelines and the ORR will be presented for all subjects. Where applicable, summary data of PFS, OS, and durability of response will be determined using Kaplan-Meier methodology; otherwise, a listing by-subject will display the data obtained. Two-sided confidence intervals will be computed for the ORR. Descriptive statistics will be performed for different patient populations.

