	
• The per protocol population will be followed from the first date of treatment up to 2 years for overall survival. Estimates of the single arm hazard rate will be determined and compared with historical control estimates 
All populations for analyses and the types of analyses to be performed will be defined in more detail in the statistical analysis plan (SAP).
 
Secondary endpoints include:
 
• The OS rate will be determined for 6, 12, 18 and 24 months using a binomial estimate of subjects surviving for at least the amount of time established by the cutpoint• PFS, and rate of pseudo-progression (PSP) of Ad-RTS-hIL-12 + veledimex when administered in combination with cemiplimab-rwlc• ORR of Ad-RTS-hIL-12 + veledimex when administered in combination with cemiplimab-rwlc at 6, 12, 18 and 24 months• Tumor response rate of Ad-RTS-hIL-12 + veledimex when administered in combination with cemiplimab-rwlc at 6, 12, 18 and 24 months• [REDACTED] 
Tumor Response Assessments:
 
The Per Protocol Population will be evaluated for ORR, PFS, PSP, and OS. Tumor response will be assessed both locally and at an independent central imaging lab using the iRANO criteria. Copies of all scans will be provided to the independent central imaging lab for determination of tumor response. Final progression determinations will be made by the independent central imaging lab. Every effort should be made to continue study therapy until disease progression is confirmed per iRANO criteria. In the instance that a subject is withdrawn from study treatment due to investigator determined progression, efforts will be made to encourage obtaining additional to confirm disease progression.
 
• Tumor response will be evaluated radiographically using MRI scans to determine tumor response and to assess the time of objective disease progression
--	--

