Sample Size Determination	
We plan to accrue up to 36 subjects to obtain approximately 25 subjects evaluable for efficacy. This subject population will be heterogeneous and as such, it is difficult to define a clear safety threshold for evaluation in combination with determination of OS, ORR and PFS at 12 weeks. A sample size of approximately 25, will allow us to estimate an overall safety rate with a maximum 95% exact confidence interval half-width of approximately 0.19. Note: a minimum of 20 subjects undergoing subtotal resection will be required to ensure that enough subjects have measurable disease for evaluation of overall response rate per iRANO criteria.
 
In addition, a toxicity boundary based on repeated significance testing provides a guideline for stopping the trial if the number of subjects experiencing unacceptable toxicity exceeds the proportions below, assuming a 30% toxicity rate is acceptable and 60% would be unacceptable:
 
Low boundary: 3/5 5/10 8/15 9/20 11/25
 
High boundary: 3/5 6/10 8/15 10/20 11/25
 
Note: A sample size of 25 to 30 subjects provides for an estimate of OS at a point in time with (at most) a 10% standard error of the estimate assuming the binomial estimation method.

Study Duration	
The duration of this study from the time of initiating subject screening until the completion of survival follow-up is anticipated to be approximately 36 months, including 12 months for enrollment and 24 months of follow-up.
 
The start of study is defined as the date when the first subject is consented into the study and the study stop date is the date of the last subject's last visit.

Table 1: Schedule of Study Procedures

Activity	Screening	Treatment							
	Day -30 to -8*	Day -7 **	Day 0 ^a	Day 1	Day 2	Day 3	Day 4 to 6	Day 7	Day 8 to 13
Informed consent	X								
Medical/Cancer history ^d	X								
Physical exam ^e , including targeted neurological exam	X	X	X	X	X	X		X	
Karnofsky PS ^f	X	X	X						
Height (screen) and weight	X							X	
Vital signs ^g	X	X	X	X	X	X		X	
Adverse events ^h									CONTINUOUS
Concomitant medications ^h									CONTINUOUS
Survival status ⁱ									CONTINUOUS
Pregnancy test ^j	X	X	X						
Hematology ^k	X	X	X ^a	X	X	X		X	
Coagulation ^l	X		X ^a	X		X		X	
Serum chemistry ^m	X	X	X ^a	X	X	X		X	
Urinalysis ⁿ	X	X	X ^a			X		X	
Thyroid panel ^o	X								
ECG ^p	X		X			X		X	
Confirm eligibility		X ^q							
Cemiplimab-rwlc dose ^q		X							
Ad-RTS-hIL-12			X ^{r,s}						

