4.5.3. Per Protocol (PP)

The per protocol population will comprise subjects who have received Day -7 of cemiplimab, the injection of Ad-RTS-hIL-12 with at least one post IL-12 dose of veledimex, at least one post IL-12 dose of cemiplimab (e.g., Day 15), and who have not had a major protocol deviation for which the key efficacy endpoints could be regarded as confounded or uninterpretable. Subjects who have had minor protocol deviation(s) that are thought not to impact efficacy will be included in this analysis population. Estimates of the overall OS hazard rate, the OS at prespecified timepoints, PFS and the ORR will be based on the PP population.

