4.7.1. Overview of Statistical Summaries by Defined Populations

Subject populations will be evaluated and used for presentation and analysis of the following:

- The FAS will be used for summaries of subject disposition, baseline characteristics and for safety. In addition, the FAS will be used in secondary analyses of OS, ORR, and PFS.
- The PP population is to be used for the primary analysis of OS, ORR, PFS and OS.
- When applicable the ESP will be used for analysis of dose limiting toxicities.
- [REDACTED]

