8.3.4. Tumor Response Rate

- Determination of tumor response will be performed on each subject in the PP population.
- The Tumor response rate of Ad-RTS-hIL-12 + velevidemex when administered in combination with cemiplimab will be estimated at 6, 12, 18 and 24 months.
- Tumor response will be defined by radiographic and clinical criteria. Complete response (CR) or partial response (PR) will be first assessed by radiographic changes that indicate a reduction of bi-dimensional tumor size as per Recist 1.1 criteria. In addition, changes in neurologic function and steroid use will be considered to determine stable disease (SD).

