Table 14.2.1.1	Objective Response Rate	Per Protocol Population	ORR					
Table 14.2.1.2	95% Confidence Intervals for Overall Response	Per Protocol Population	ORRci					
Table 14.2.2	Progression Free Survival	Per Protocol Population	PFS					
Table 14.2.3	Time to Overall Survival in Months	Per Protocol Population	OS			SS	ADTTE	
Table 14.2.3.1	OS for 20mg group 1 main study and 20 mg expansion for patients characteristics subgroups	Per Protocol Population	OSCAT					

Table 14.3.1.1	Overall TEAEs Summary	Full Analysis Population	AEoverall			AE	ADAE	AeOverall is done
Table 14.3.1.2	Treatment Emergent Adverse Events by System Organ Class and Preferred Term	Full Analysis Population	AEs			AE	ADAE	AEs tables are done
Table 14.3.1.3	Treatment-Related Adverse Events by System Organ Class and Preferred Term	Full Analysis Population	AEs			AE	ADAE	AEs tables are done
Table 14.3.1.4	Adverse Events Leading to Study Discontinuation by System Organ Class and Preferred Term	Full Analysis Population	AEs			AE	ADAE	AEs tables are done
Table 14.3.1.5	Adverse Events Leading to Discontinuation of Study Medication by System Organ Class and Preferred Term	Full Analysis Population	AEs			AE	ADAE	AEs tables are done
Table 14.3.1.6	Adverse Events Leading to Interruption of Study Medication by System Organ Class and Preferred Term	Full Analysis Population	AEs			AE	ADAE	AEs tables are done
Table 14.3.1.7	Adverse Events Leading to Dose Reduction of Study Medication by System Organ Class and Preferred Term	Full Analysis Population	AEs			AE	ADAE	AEs tables are done

Table 14.3.1.8	Adverse Events Leading to Death by System Organ Class and Preferred Term	Full Analysis Population	AEs			AE	ADAE	AEs tables are done
Table 14.3.1.9	Treatment Emergent Adverse Events by System Organ Class, Preferred Term and Severity	Full Analysis Population	AEs			AE	ADAE	AEs tables are done
Table 14.3.1.10	Treatment Emergent Adverse Events by System Organ Class, Preferred Term and Severity with CTCAE Toxicity Grade ≥ 3	Full Analysis Population	AESev			AE	ADAE	AESev tables are done
Table 14.3.1.11	Serious Adverse Events by System Organ Class and Preferred Term	Full Analysis Population	AESev			AE	ADAE	AESev tables are done
Table 14.3.1.12	Treatment Emergent Adverse Events by Preferred Term in Decreasing Frequency	Full Analysis Population	AEPT			AE	ADAE	AEPT tables are done

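### ORR has no visible measurable-disease denominator although gross total resection is allowed, so it may be diluted by subjects who had nothing to measure at baseline

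*Protocol*

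**What the plan says.** **Who is analysed.** Protocol 16.6.4 states that "the ORR will be presented for all subjects". The synopsis adds: "The Per Protocol Population will be evaluated for ORR, PFS, PSP, and OS". Protocol 16.5 adds: "Secondary analyses for all efficacy endpoints will be based on the Safety population". The SAP follows the same pattern: "PFS and the ORR will be based on the PP population" (4.5.3), "the FAS will be used in secondary analyses of OS, ORR, and PFS" (4.7.1) and "Determination of tumor response will be performed on each subject in the PP population" (8.3.4). PP membership depends on doses received and the absence of a major deviation or violation (Protocol 16.1, SAP 4.5.3). Measurable disease is not a condition.

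**Who can be assessed.** The vector is injected after a subtotal or gross total resection (Protocol 8.1). The baseline scan for response is taken after surgery: within 24 hours of injection plus a 48-hour window (Protocol 13.1), or within 72 hours after it (SAP 11.2). CR and PR start from a reduction in bidimensional tumour size (Protocol 13.1, SAP 8.3.4). The synopsis recognises the consequence: "a minimum of 20 subjects undergoing subtotal resection will be required to ensure that enough subjects have measurable disease".

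**Whether ORR is reported.** SAP 10.1 and 10.2.4 remove ORR from the final analysis. The table lists in the SAP appendices still carry a table titled "Objective Response Rate" and a companion confidence-interval table, both for the PP population.

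**The concern.** The sponsor accepts that response evaluation needs measurable disease and sets a recruitment minimum for that reason, but no analysis section carries the condition into the ORR denominator. A subject with nothing measurable on the post-operative scan has nothing that can shrink. If that subject stays in the denominator, the rate falls for a reason unrelated to treatment, and the fall depends on how many complete resections happened to be done.

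This is a single-arm study whose estimates are to be set against historical control data where applicable (Protocol 16, SAP 8). A response rate that moves with the surgical mix is hard to place beside a rate from patients who all had measurable disease.

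**Working it through.** The documents give no ORR target, ORR precision or ORR sample size, so there is no stated ORR figure to reproduce. The check is a dilution calculation.

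**Inputs from the documents**
- At least 20 subtotal resections (Protocol synopsis, Sample Size Determination).
- About 25 evaluable for efficacy from up to 36 accrued (Protocol 16.2).
- 40 treated subjects in the FAS (SAP 4.4).

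**Assumptions**
- m subjects have measurable disease at baseline. m is not given; m = 20 is the illustration.
- p is the ORR among those m subjects. It is not given; 10% to 40% is shown.
- The other N − m subjects stay in the denominator and contribute no responses.

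**Formula.** ORR over the full set = p × m/N, so the dilution factor is m/N.

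| Set | m/N | Factor | p = 10% | p = 20% | p = 30% | p = 40% |
|---|---|---|---|---|---|---|
| Planned PP, about 25 | 20/25 | 0.80 | 8% | 16% | 24% | 32% |
| All 36 planned | 20/36 | 0.56 | 5.6% | 11.1% | 16.7% | 22.2% |
| FAS, 40 | 20/40 | 0.50 | 5% | 10% | 15% | 20% |

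**Range within PP**
- If every PP subject has measurable disease, the factor is 25/25 = 1.0 and there is no dilution.
- The minimum of 20 is not stated to apply within PP. With 36 accrued and 20 subtotal, up to 36 − 20 = 16 could be gross total. If all 16 were in PP and none had measurable disease, m = 25 − 16 = 9 and the factor is 9/25 = 0.36. This is an extreme case.

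**Effect on the interval.** The same 4 responders, with exact (Clopper-Pearson) 95% intervals:
- 4/20 = 20.0% (5.7% to 43.7%)
- 4/25 = 16.0% (4.5% to 36.1%)
- 4/36 = 11.1% (3.1% to 26.1%)
- 4/40 = 10.0% (2.8% to 23.7%)

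The interval on 20 measurable subjects is 43.7 − 5.7 = 38.0 points wide, against 36.1 − 4.5 = 31.6 points on 25.

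**Is the denominator settled elsewhere in the SAP?** No. Its general rules conflict: the whole analysis set (4.6), non-missing data only (4.7 and 11.1), and missing responses included (4.7 and 11.7). SAP 8.3.5 gives best overall response a Not Evaluable category, and a No Response category for subjects without an assessment, but does not say how either enters ORR.

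**The case against.** There is a good case on the other side, and most of it limits the size of the point without removing it.

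- **ORR may never be reported.** SAP 10.2.4 drops it. The table lists that keep it are weak evidence of survival: they also keep vital-sign, neurological and ECG tables that SAP 10.6 drops. This stands. The two parts of the SAP contradict each other and must be reconciled, and ORR remains a protocol secondary endpoint.
- **A reader might infer that every gross-total-resection subject cannot respond.** The documents do not support that. Multifocal disease with up to 5 enhancing lesions is allowed (Protocol 9.1), and measurable lesions other than the injected one are followed (Protocol 13.1).
- **A reader might infer that unmeasurable subjects are certainly counted as non-responders.** No text says so. Under the non-missing rule some could drop out. The whole-set rule in SAP 4.6 and the No Response label make dilution the likelier reading, but not a certain one.
- **An all-subject denominator is conservative, not a mistake.** Agreed. Its interval is valid for that quantity, and no formal testing is planned. The weakness is that it is the only rate planned. Protocol 16.6.4 promises descriptive statistics for different populations, which leaves room for a measurable subset but does not define one.
- **Relevant text may be hidden.** One population bullet in Protocol 16.1 is redacted and no SAP 4.5.5 is visible. An earlier protocol version in the same file shows a biomarker set in that place, so a response-evaluable set there is unlikely but not excluded. The Imaging Charter and the iRANO text are also not available.

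**Conclusion.** The point holds in a limited form. As written, the plan calculates ORR in sets that can include subjects with no measurable disease at baseline, while the protocol itself ties response evaluation to measurable disease. ORR may therefore be diluted.

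The size is unknown. For the planned PP set, which is the main ORR set, the factor is 0.80 if 20 of about 25 are measurable, 1.0 if all are, and lower than 0.80 if fewer than 20 are. It would be tempting to conclude that the reported ORR will be about half the true rate. The documents do not support that: 0.56 and 0.50 belong to 36 accrued and 40 treated subjects, and both combine those totals with an assumed 20 measurable. Thirty-six is an accrual ceiling, and the FAS is secondary for ORR.

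All of this assumes that ORR is reported, that unmeasurable subjects stay in the denominator, and that no redacted population definition already deals with them. It is a cheap improvement to a secondary endpoint and does not affect the primary OS analysis.

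**What to change.** 1. Define a response set: PP subjects, and FAS subjects as secondary, with measurable enhancing disease on the post-operative baseline MRI. Define it by the scan, not by type of resection.
2. Report ORR and tumour response rate in that set with exact 95% confidence intervals.
3. Keep the all-subject rate beside it as the conservative figure, and give the number of subjects with no measurable baseline disease.
4. State how Not Evaluable and No Response count in each rate, overriding the conflicting general denominator rules.
5. Reconcile SAP 10.2.4 with the table lists. If ORR is dropped, remove its tables; if it is kept, apply items 1 to 4.

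The cost is a few sentences in the SAP and one flag from lesion data that the listings already cover. The downside is a smaller denominator and a wider interval for the new rate.

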16.6.5. Multi-Center Study

Tumor response and safety data will be presented over all study centers.

16.6.6. Adjustments for Covariates

No adjustments for covariates will be made.

